2.8.4.2 Vital signs

Vital sign measurements include sitting systolic and diastolic blood pressures, sitting pulse, body temperature, height and body weight.

Three sitting measurements of blood pressure (SBP and DBP) and pulse will be taken at each vital sign assessment.

For post-baseline assessments, the blood pressure and pulse values will be the average of the non-missing values of the 3 measurements. If more than one blood pressure/pulse assessment (scheduled or unscheduled) exists in a particular visit-window (as defined in [Section 2.1.2.1](#)),

derivation should follow the rules as defined in [Section 2.1.2.3](#). Derivation of baselines for blood pressure and pulse are provided in [Section 2.1.1](#).

Height will be collected at screening visit only and will only be summarized as demographics. Analyses of vital sign measurements (excluding data collected on Day 1 protocol scheduled visit) using descriptive summary statistics (mean, median, standard deviation, min, max) for the change from baseline for each post-baseline visit-window will be performed. These descriptive summaries will be presented by vital sign parameter and age group. Change from baseline will only be summarized for subjects with both baseline and post-baseline values and will be calculated as:

$$\text{change from baseline} = \text{post-baseline value} - \text{baseline value}$$

The number and percentage of subjects with clinically notable vital signs (at any time post-baseline) will be presented by age group. Listings of clinical notable vital signs during treatment period will be presented by age group.

Clinical notable vital signs values are defined in the table below.

Table 2-11 Vital signs clinically notable values

NOTABLE VITAL SIGNS AND BODY WEIGHT		
Vital Sign Variable	Age	Notable Criteria
Heart Rate (bpm)	< 12 years	>130bpm or Increase of ≥ 15 bpm from baseline Or < 70bpm or Decrease of ≥ 15 bpm from baseline
	≥ 12 years	>120bpm or Increase of ≥ 15 bpm from baseline Or < 50bpm or Decrease of ≥ 15 bpm from baseline
Systolic BP (mmHg)	< 12 years	≥ 125 mmHg or Increase of ≥ 20 mmHg from baseline Or ≤ 70 mmHg or Decrease of ≥ 20 mmHg from baseline
	≥ 12 to < 18 years	≥ 160 mmHg or Increase of ≥ 20 mmHg from baseline Or ≤ 90 mmHg or Decrease of ≥ 20 mmHg from baseline
	≥ 18 years	≥ 180 mmHg or Increase of ≥ 20 mmHg from baseline Or ≤ 90 mmHg or Decrease of ≥ 20 mmHg from baseline
Diastolic BP (mmHg)	< 12 years	≥ 85 mmHg or Increase of ≥ 15 mmHg from baseline Or ≤ 50 mmHg or Decrease of ≥ 15 mmHg from baseline
	≥ 12 to < 18 years	≥ 95 mmHg or Increase of ≥ 15 mmHg from baseline Or ≤ 50 mmHg or Decrease of ≥ 15 mmHg from baseline
	≥ 18 years	≥ 105 mmHg or Increase of ≥ 15 mmHg from baseline Or ≤ 50 mmHg or Decrease of ≥ 15 mmHg from baseline
Temperature (°C)	All	>38.3 °C/ 101°F
Body weight (kg)	All	$\pm 7\%$ from baseline weight

For first dose administration monitoring, pulse, sitting systolic, diastolic blood pressures and their change from pre-dose will be summarized by timepoint and age group during 1st and 2nd dose (if necessary) administration. Boxplots on these three parameters will also be provided as graphical presentation. The number and percentage of subjects with clinically notable values for these three parameters (at any timepoint post-dose during 1st and 2nd dose (if necessary) administration) will also be presented by age group (or listing for the Child group if more appropriate).

For the patients who missed the visits, but took off-site vital sign measurements due to COVID19 (lockdown, site issue, subject concern or other), the off-site vital sign data will be included to analyze. The sensitivity analysis will be conducted to assess vital sign data (heart rate, SBP and DBP), with the only change to exclude off-site vital sign data. For this sensitivity analysis, number and percentage of patients with clinically notable vital sign abnormalities and patients with clinically notable vital sign values at any timepoint post-dose during first/second dose administration by age group will be presented.

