16.1 Appendix 1: Clinically notable laboratory values and vital signs

Table 16-1 Criteria For Notable Laboratory Abnormalities

Notable Values		
Laboratory Variable	Standard Units	SI Units
Serum glutamic oxaloacetic transaminase (SGOT) (AST)	>82 U/L	>82 U/L
Serum glutamic pyruvic transaminase (SGPT) (ALT)	>90 U/L	>90 U/L
Total bilirubin	≥ 2.0 mg/dL	≥ 34.2 µmol/L
RENAL FUNCTION / METABOLIC VARIABLES		
Creatinine	≥2.0 mg/dL	≥176umol/L
Cholesterol	≥ 240 mg/dL	≥ 6.21 mmol/L
Triglycerides	≥ 300 mg/dL	≥ 3.39 mmol/L
HEMATOLOGY VARIABLES		
Hemoglobin	≤ 10.0 g/dL	≤ 100g/L
Platelets (Thrombocytes)	≤ 100 k/mm ³	≤ 100 x 10 ⁹ /L
	≥ 600 k/mm ³	≥ 600 x 10 ⁹ /L
Leukocytes (WBCs)	≤ 2.0 k/mm ³	≤ 2.0 x 10 ⁹ /L
	≥ 15 k/mm ³	≥ 15x 10 ⁹ /L
HEMATOLOGY VARIABLES: DIFFERENTIAL		
Granulocytes (Poly, Neutrophils)	≤ 1,000/mm ³	≤ 1 x 10 ⁹ /L
	≥12000/mm ³	≥ 12 x 10 ⁹ /L
Lymphocytes	<200/mm ³	<0.2 x 10 ⁹ /L
	≥8000/mm ³	≥8 x 10 ⁹ /L
Red blood cells (RBCs)	<3,300,000/mm ³	<3.3 x 10 ¹² /L
	>6,800,000/mm ³	>6.8 x 10 ¹² /L

NOTABLE VITAL SIGNS AND BODY WEIGHT	
Vital Sign Variable	Notable Criteria
Pulse (beats/min)	>120bpm or Increase of ≥ 15bpm from baseline Or < 50bpm or Decrease of ≥ 15bpm from baseline
Systolic BP (mmHg)	≥ 160 mmHg or Increase of ≥ 20mmHg from baseline Or ≤ 90 mmHg or Decrease of ≥ 20mmHg from baseline
Diastolic BP (mmHg)	≥ 100 mmHg or Increase of ≥ 15mmHg from baseline Or ≤ 50 mmHg or Decrease of ≥ 15mmHg from baseline
Temperature (°C)	>38.3 °C/ 101°F

Body weight (kg)	$\pm 7\%$ from baseline weight
------------------	--------------------------------

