16.7 Appendix 7 Guidance on safety monitoring

Guidance on monitoring of patients with elevated blood pressure

Participants who have at least two out of the three sitting readings of blood pressure (systolic BP ≥ 140 and/or diastolic BP ≥ 90 mmHg) should be recommended referred to his primary care physician, an independent internist or to the specialty hypertension clinic for evaluation, diagnosis and treatment of hypertension. Participants with BP values of $> 160/100$ mmHg on any visit during the study should be immediately referred as above for evaluation, diagnosis and treatment of hypertension. Newly diagnosed hypertension as well as an aggravation of a pre-existing condition must be reported as an AE and discontinuation of the study drug may be considered by the investigator.

Guidance on monitoring of participants with elevated liver function tests

Table 16-3 Liver event and laboratory trigger definitions

	Definition/ threshold
Liver laboratory triggers If ALT, AST and total bilirubin normal at baseline:	
 ALT or AST $> 5 \times$ ULN ALP $> 2 \times$ ULN (in the absence of known bone pathology) Total bilirubin $> 3 \times$ ULN (in the absence of known Gilbert syndrome) ALT or AST $> 3 \times$ ULN and INR > 1.5 Potential Hy's Law cases (defined as ALT or AST $> 3 \times$ ULN and Total bilirubin $> 2 \times$ ULN [mainly conjugated fraction] without notable increase in ALP to $> 2 \times$ ULN) Any clinical event of jaundice (or equivalent term) ALT or AST $> 3 \times$ ULN accompanied by (general) malaise, fatigue, abdominal pain, nausea, or vomiting, or rash with eosinophilia Any adverse event potentially indicative of a liver toxicity*
If ALT or AST abnormal at baseline:	
 ALT or AST $> 2 \times$ baseline or > 300 U/L (whichever occurs first)

*These events cover the following: hepatic failure, fibrosis and cirrhosis, and other liver damage-related conditions; non-infectious hepatitis; benign, malignant and unspecified liver neoplasms ULN: upper limit of normal

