2.8.5.4 Data summaries

Summaries on the FTY SAF set by treatment group include:

- Frequency (%) distribution of categorized sitting pulse or change (or percent change) from pre-dose sitting pulse during first dose administration (note that categories are given in table shells)
- Summary of the overall dose monitoring experience (1st dose, 2nd dose (if necessary), and restart dose (if applicable))
- Incidence of notable vital sign abnormalities based on the notable criteria in [Table 2-8](#) (1st dose and 2nd dose (if necessary))
- Summary statistics and changes from pre-dose in ECG parameters by time point during 1st and 2nd dose (if necessary) administration
- Incidence of abnormal QTc interval as defined by the abnormality criteria in [Table 2-10](#) during 1st and 2nd dose (if necessary) administration

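### The SAP's adult notable blood-pressure limits (180/105 mmHg) sit above the protocol's (160/100 mmHg), so the adult notable-BP percentage can only equal or understate the protocol-defined one

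*SAP*

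**What the plan says.** **Protocol.** Section 8.4 (Table 8-2) refers to Appendix 1 for the definition of clinically notable vital signs, and Section 12.5.1 plans to present vital signs by those ranges. Appendix 1 (Section 16.1) gives one set of limits for all ages. Systolic pressure is notable on the high side at "≥ 160 mmHg or Increase of ≥ 20mmHg from baseline" and diastolic at "≥ 100 mmHg or Increase of ≥ 15mmHg from baseline". Separately, Appendix 7 (Section 16.7) says that participants above 160/100 mmHg at any visit "should be immediately referred as above for evaluation, diagnosis and treatment of hypertension".

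**SAP.** Section 1 states that the SAP is consistent with the protocol. Table 2-11 in Section 2.8.4.2 splits the limits by age. For participants aged 18 or over the high-side systolic criterion is "≥ 180 mmHg or Increase of ≥ 20 mmHg from baseline" and the diastolic one is "≥ 105 mmHg or Increase of ≥ 15 mmHg from baseline". The table feeds the number and percentage of subjects notable at any time post-baseline, by age group, and a listing.

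Section 2.8.5.4 plans, for first- and second-dose monitoring, "Incidence of notable vital sign abnormalities based on the notable criteria in" Table 2-8. Table 2-8 holds laboratory limits and no vital signs.

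**The concern.** The same term has two definitions. The SAP raises the absolute high limit for adults only. Ages 12 to under 18 keep systolic 160 and get a lower diastolic limit (95), and the under-12 limits are lower still. The adult fall, rise and low-value criteria match the protocol. An adult can therefore be notable under the protocol, and above the level at which it asks for immediate referral, without meeting the SAP's high-BP criteria.

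Protocol Section 1.1 lists hypertension among the safety areas of note for this drug and expects a mean rise of about 3 mmHg systolic and 2 mmHg diastolic. A typical on-drug change is thus far below the 20/15 mmHg rise criterion. For adults who start high, the absolute limit does most of the work, and it is the part that was raised. At stake is whether the adult notable-BP percentage means what the protocol says it means.

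**Working it through.** **1. Adult criteria side by side**

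| Criterion | Protocol Appendix 1 | SAP Table 2-11, age 18 or over |
|---|---|---|
| Systolic, high | ≥160 | ≥180 |
| Systolic, rise / fall from baseline | ≥20 / ≥20 | ≥20 / ≥20 |
| Systolic, low | ≤90 | ≤90 |
| Diastolic, high | ≥100 | ≥105 |
| Diastolic, rise / fall from baseline | ≥15 / ≥15 | ≥15 / ≥15 |
| Diastolic, low | ≤50 | ≤50 |

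**2. Direction.** All criteria but the high limit are identical, and the SAP's high limit is stricter. Every adult notable under the SAP is therefore notable under the protocol, but not the reverse. The SAP percentage is equal or lower. This needs no distributional assumption.

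**3. Who is lost.** Let b be the baseline and v the post-baseline value.

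- Systolic: v is missed on the high side when 160 ≤ v < 180 and v − b < 20. Then b > v − 20 ≥ 140, so only baselines above 140 are affected.
- Diastolic: v is missed when 100 ≤ v < 105 and v − b < 15. Then b > v − 15 ≥ 85, so only baselines above 85 are affected.

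In whole numbers, a systolic baseline of 141 loses only a reading of 160, a baseline of 150 loses 160–169, and a baseline of 159 loses 160–178. A diastolic baseline of 86 loses only 100, and baselines of 90–99 lose all of 100–104.

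Example: an adult goes from 155/95 to 168/103. The rises are 13 and 8, below 20 and 15. The reading exceeds 160/100 but is under 180/105. It is notable under the protocol and not under the SAP.

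Eligibility (protocol Section 5.2) excludes uncontrolled hypertension without a number, so such baselines are possible.

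**4. Size, each pressure separately (illustration).** From the documents: mean change +3/+2 mmHg (protocol Section 1.1) and nine post-baseline visits in the treatment period (protocol Table 8-1). Assumed, because the documents give no values: normal distributions; systolic baseline mean 118–125, between-person SD 12–15, within-person SD 6–10; diastolic baseline mean 75–78, SD 9–10, within-person SD 5–6. Whole-number readings and all criteria in the table above were applied.

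| Result | Systolic | Diastolic |
|---|---|---|
| Of adults ever ≥160 / ≥100, share never flagged by the SAP rule | about 16–74% | about 27–45% |
| Protocol-defined notable percentage | about 20–73% | about 30–52% |
| Fall in that percentage under the SAP rule | about 0.6–5.3 points | about 2.3–5.0 points |

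If only the high-side criteria count as a flag, the missed shares are about 35–79% and 36–51%, and the fall is about 0.6–6 points.

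**5. Both pressures together (illustration).** This used assumed baseline means of 115–125/75–80, between-person SDs of 12–15/8–10, within-person SDs of 6–9/4–6 and a correlation of 0.6. Between 2% and 26% of adults ever exceed 160 or 100, about 15–60% of them are never notable under the SAP, and the overall notable proportion falls by about 1 to 8 points. One scenario (means 120/78, SDs 14/9, within-person SDs 6/4) shows how the figures fit: 8.16% exceed the limits and 55.4% of those are missed, so 0.0816 × 0.554 = 0.045. The notable proportion falls from 0.310 to 0.265, which is also 0.045.

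**6. After the change.** With 160/100 in the adult rows the two definitions coincide and the missed set is empty.

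**The case against.** The strongest points against are these.

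- **Other routes capture the event.** Appendix 7 requires new or aggravated hypertension to be reported as an adverse event, SAP 2.8.1 tabulates those events, and change-from-baseline summaries remain. Site referral does not depend on a SAP table. This stands: the loss is confined to the notable-value outputs.
- **No decision turns on the percentage.** The study is single-arm and descriptive, without hypothesis tests. This stands and limits the weight of the point.
- **Referral and notability differ within the protocol itself.** Appendix 7 recommends referral at 140/90 on two of three readings, below the absolute notable limit. The referral rule is also strictly above 160/100, so readings of exactly 160 or 100 are notable without falling under it. This stands. The referral rule shows what the missed readings are, but the case rests on the two definitions of notable.
- **Age-banded limits may be deliberate.** Limits that rise with age are not an error in themselves, and the minors' high-side limits are as strict as or stricter than the protocol's. This stands, but it does not reconcile the adult rows with the definition the protocol names.

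A reader might also infer more than the documents support:

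- **That any adult starting at 145–159 and reaching 160–179 is missed.** Of the 15 × 20 = 300 whole-number pairs in that range, the 20 mmHg rise still flags 160 − b readings for each baseline b, that is 15 + 14 + … + 1 = 120 (40%).
- **That the 6.5% versus 3.3% hypertension figure in protocol Section 1.1 would be biased.** That is an adverse-event rate, which Table 2-11 does not touch.
- **That nearly the whole sample is affected.** The adult share is not stated; protocol Section 4.1 leaves paediatric numbers to natural occurrence.
- **That the change was made without declaring it.** SAP Section 4 is redacted, so this cannot be judged.

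**Conclusion.** The inconsistency is real and its direction is certain: the adult notable-BP percentage in the SAP can only be equal to or lower than the protocol-defined one. The gap affects adults with a baseline above 140 systolic or above 85 diastolic whose reading falls between the two limits without a 20/15 mmHg rise. Its size is uncertain, because only the mean change on drug comes from the documents. Under the assumed distributions it is about 0.6 to 5 percentage points per parameter with all criteria counted. This is a moderate reporting fault that should be corrected before the outputs are produced. It does not threaten the safety data as a whole, and it implies no judgement on which blood-pressure limit is clinically right. The reference to Table 2-8 in SAP 2.8.5.4 is plainly wrong.

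**What to change.** 1. Reconcile SAP Table 2-11 with protocol Appendix 1. For participants aged 18 or over, tabulate by the protocol-defined 160/100 limits with the existing change and low-value criteria. Keep 180/105 as an additional row if wanted.
2. If the redacted SAP Section 4 does not already do so, state there that the age-specific rows differ from the protocol, and why.
3. In SAP 2.8.5.4, cite Table 2-11 instead of Table 2-8.

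**Cost.** A small SAP edit, plus reruns of the notable vital-sign table and listing, the first/second-dose notable table, the two COVID-19 off-site sensitivity tables and the listing after last administration (SAP 2.8.6). No new data are needed. The adult notable-BP percentage may come out slightly less favourable.

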2.8.4.3 Ophthalmic evaluations

If any subject reports a TEAE of macular edema (occurs after first dose and before safety cutoff), a listing with assessments of optical coherence tomography (OCT) at the time of screening, diagnosis and resolution (if resolved) will be provided. This listing can be omitted if no such subject in the study.

2.8.4.4 Dermatology evaluations

If any subject reports a TEAE of skin lesions (occurs after first dose and before safety cutoff), a listing with skin lesions will be provided. This listing can be omitted if no such subject in the study.

2.8.5 First dose (second dose/restart dose) monitoring

Any cases where restarting first dose monitoring after study drug interruption was required but was not performed will be reported as a PD.

2.8.5.1 Vital signs

Hourly vital signs including pulse, SBP and DBP are collected for the first dose, second dose (if necessary), and restarting of dose after interruption (if applicable).

2.8.5.2 ECG

ECG will be performed at pre-dose, 6 hours post dose, and >6 hours post dose during the first dose, second dose (if necessary), and restarting of dose after interruption (if applicable).

2.8.5.3 Dose monitoring experience

The first dose/second dose (if necessary) /restart dose (if applicable) monitoring experience refers to the information collected on the dose administration monitoring eCRFs (e.g. whether subjects are discharged after 6 hours post-dose or extended monitoring is required after 6 hours

post-dose, whether subjects are hospitalized, whether subjects discontinue the study drug permanently, and whether SAE is reported, etc.).

All data with yes/no responses will be summarized.

2.8.5.4 Data summaries

Summaries on the FTY SAF set by treatment group include:

- Frequency (%) distribution of categorized sitting pulse or change (or percent change) from pre-dose sitting pulse during first dose administration (note that categories are given in table shells)
- Summary of the overall dose monitoring experience (1st dose, 2nd dose (if necessary), and restart dose (if applicable))
- Incidence of notable vital sign abnormalities based on the notable criteria in [Table 2-8](#) (1st dose and 2nd dose (if necessary))
- Summary statistics and changes from pre-dose in ECG parameters by time point during 1st and 2nd dose (if necessary) administration
- Incidence of abnormal QTc interval as defined by the abnormality criteria in [Table 2-10](#) during 1st and 2nd dose (if necessary) administration

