A key pharmacodynamic effect of fingolimod is a dose-dependent reduction of peripheral lymphocyte count to 20 - 30% of baseline values. This is due to the reversible sequestration of lymphocytes in lymphoid tissues. In multiple sclerosis clinical trials, the overall rate of infections (65.1%) at the 0.5 mg dose was similar to placebo [Novartis 2019](#). However, bronchitis, herpes zoster and pneumonia, were more common in Gilenya treated patients [Karlsson G,Francis and Schmouder R,et 2009](#). Serious infections occurred at a rate of 1.6% in the fingolimod 0.5 mg group versus 1.4% in the placebo group [\(2013\) 2.5 Clinical Overview Rationale for changes to Core Data Sheet \(CDS\) / A full review and up date of sections, A full review and update of sections, “Warnings and Precautions”, “Adverse Drug Reactions” and “Interactions”](#) . In a second 2-year placebo controlled study, CFTYD2309, which was reported after approval of fingolimod, the safety profile seen in prior studies was largely confirmed, however in this study herpes zoster was reported more frequently in the fingolimod arms as compared to placebo (2.5% vs. 0.8% respectively) and basal cell carcinomas were more frequent in the fingolimod 0.5 mg group (2.8%) as compared to both, the fingolimod 1.25 mg and the placebo arms (1.6 and 0.6%) respectively. One fatal primary disseminated varicella zoster infection and one fatal herpes simplex encephalitis case have occurred in patients receiving the 1.25 mg/day dose; at the fingolimod 0.5 mg dose, one patient died in the post-marketing setting due to a disseminated varicella zoster infection in the context of high dose steroid treatment.

As part of a post-approval commitment to China's health authorities, Novartis is conducting this post-approval commitment study (PAC) in order to evaluate the efficacy and safety profile of fingolimod in Chinese multiple sclerosis patients. The study will collect safety profile information related to clinical practice setting and long-term follow-up including, but not limited to infections, cardiac and vascular events (e.g. stroke, myocardial infarction, angina pectoris and peripheral vascular disease, second and third degree AV conduction block, hypertension), malignancies, pulmonary events, seizures, MS relapses, atypical severe neurological events and sudden/unexplained death.

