12.5.1 Safety endpoints

For all safety analyses, the safety set will be used.

Safety assessments will include: adverse events (AEs), laboratory tests, vital signs, ophthalmic examinations, dermatology assessment, and ECG data.

An AE will be considered as treatment-emergent adverse event (TEAE) if it starts on or after first treatment with fingolimod during the study. TEAE will be summarized by presenting the number and percentage of participants experiencing adverse events by system organ class (SOC), preferred term (PT) and severity of adverse events.

Severe AEs, serious AEs, drug related AEs and the AEs leading to premature discontinuation of study drug will be presented in a similar format as adverse events.

Laboratory and vital sign data will be presented by clinical notable ranges.

The clinical notable abnormality of ophthalmic and dermatology data will be summarized as AE.

The (uncorrected) QT interval of ECG will be corrected according to the Bazett's and Fridericia formulae and then summarized by visit. Abnormal findings from ECG will be summarized as AE as well.

For the first dose administration monitoring, the change from pre-dose of pulse rate and BP at each hour will be summarized and the individual plots over time will be provided. The incidence rate of abnormal ECG findings at pre-dose and 6 hours post-dose, as well as the corrected QT change in category from pre-dose to 6 hours post-dose will be presented.

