2.8.1 Adverse events (AEs)

An adverse event (AE) is any untoward medical occurrence (i.e. any unfavorable and unintended sign [including abnormal laboratory findings], symptom or disease) in a clinical investigation subject after providing written informed consent for participation in the study. That means that a subject can report AEs before having started study medication. For reporting purposes, the main focus will be on treatment emergent adverse event (TEAE), defined as any AE which started on or after the day of first dose of study medication or events present prior to the start of treatment but increased in severity based on preferred term.

Except for serious TEAEs and deaths, only TEAEs up to and including the safety cut-off will be included in the analyses. All serious TEAEs and deaths will be included, regardless of the safety cut-off.

TEAEs will be reported by primary system organ class (SOC) and preferred term (PT) according to the most recent Medical Dictionary for Regulatory Activities (MedDRA). The MedDRA version used for reporting the study will be specified in a footnote of the tables, figures or listings (TFLs).

Overview of TEAE will be provided. The number and percentage of subjects reporting any TEAEs (referred to as incidence of any TEAEs in the following) will be summarized by age group, primary SOC and preferred term. Separate summaries will be provided for serious TEAEs, drug related TEAEs, TEAEs leading to permanent discontinuation of study treatment, TEAEs causing study treatment interruption, and most common TEAEs ($\geq 10\%$ in any of the age groups), which could be replaced by listings (for Child or even for both Adult and Child) if more appropriate. Additionally, the incidence of any TEAEs will also be summarized by age group, primary SOC, preferred term, and maximum severity (Mild, Moderate and Severe). Missing severity will not be imputed.

If a subject reported more than one AE within the same primary SOC, the subject will be counted only once with the maximum severity at the SOCs level, where applicable.

All AEs will be presented in listings.

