2.8.4 Other safety data

2.8.4.1 ECG and cardiac imaging data

ECG data will be collected at selected scheduled visits as specified in [\[Protocol Table 8-1\]](#). Clinically significant findings from ECG evaluations will be reported as AEs and included in the analysis of AEs. ECG parameters include mean heart rate, mean PR interval, mean uncorrected QT interval, mean QRS duration, and QT corrected using Fridericia's correction formula (all as collected on the ECG CRF). Descriptive statistics of each ECG parameter will be provided for each baseline and post-baseline visit-window by age group. Similar summaries will also be provided for change from baseline ECG parameters for each post-baseline visit-window. Criteria in corrected QT interval as defined in [Table 2-10](#) will be provided for each criterion by age group (or listing for the Child group if more appropriate).

Table 2-10 Abnormality criteria for corrected QT interval

	Male subjects	Female subjects
1	>450 msec	>470 msec
2	>500 msec	> 520 msec
3	30 - 60 msec increase from Baseline	
4	>60 msec increase from Baseline	

For first dose administration monitoring, ECG parameters and change from pre-dose in ECG parameters by timepoint during 1st and 2nd dose (if necessary) administration will be summarized by age group. The number and percentage of subjects meeting the criteria in corrected QT interval (at any timepoint post-dose during 1st and 2nd dose (if necessary) administration) will be presented by age group (or listing for the Child group if more appropriate).

For non by-visit summaries, visits defined by visit-windows will not be used. All available data from scheduled and unscheduled visits will be considered.

For the patients who missed the visits, but took off-site ECG evaluations due to COVID19 (lockdown, site issue, subject concern or other), the off-site ECG data will be included to analyze. The sensitivity analysis will be conducted to assess ECG data, with the only change to exclude off-site ECG data. For this sensitivity analysis, number and percentage of patients meeting the criteria in corrected QT interval and the corrected QT interval criteria (at any timepoint post-dose during first/second dose administration) by age group will be presented.

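### The visible SAP omits the protocol's incidence of abnormal ECG findings before and 6 hours after the first dose, so first-dose AV block is counted only through the adverse-event tables

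*SAP*

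**What the plan says.** Protocol 12.5.1 names two ECG outputs for first-dose monitoring. One is "The incidence rate of abnormal ECG findings at pre-dose and 6 hours post-dose"; the other is the change in QTc category from pre-dose to 6 hours. For ECG data generally, the same section adds: "Abnormal findings from ECG will be summarized as AE as well". The adverse-event summary is thus an addition to the time-point incidence, not a substitute for it.

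SAP 2.8.5.4 lists two ECG outputs for the dosing days: "Summary statistics and changes from pre-dose in ECG parameters by time point during 1st and 2nd dose (if necessary) administration", and "Incidence of abnormal QTc interval as defined by the abnormality criteria in" Table 2-10. SAP 2.8.4.1 describes the same two kinds of output and defines the variables: "ECG parameters include mean heart rate, mean PR interval, mean uncorrected QT interval, mean QRS duration", plus Fridericia QTc. It keeps the adverse-event route: "Clinically significant findings from ECG evaluations will be reported as AEs and included in the analysis of AEs".

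Protocol 1.1 includes "second and third degree AV conduction block" among the events on which the study will collect safety information. Protocol 4.5 gives bradyarrhythmia, with conduction effects, as a risk after the first dose. SAP section 1 says the SAP agrees with the current protocol.

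**The concern.** The only ECG abnormality that the visible SAP puts into categories is QTc prolongation. The first-dose risk that the protocol names is slowed heart rate and conduction, and for conduction the SAP offers summary statistics of PR and QRS but no count of affected participants.

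The study is a post-approval commitment, and Protocol 4.1 says that no data from Chinese participants existed before it. How many participants had a new conduction abnormality on the 6-hour ECG is a natural question for the study report. The protocol planned an output that would answer it.

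**Working it through.** There is no stated figure to reproduce, so the check sets the two documents side by side.

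| Item | Protocol 12.5.1 | Visible SAP |
|---|---|---|
| Incidence of abnormal ECG findings, pre-dose and 6 h | Specified | None in 2.8.4.1 or 2.8.5.1 to 2.8.5.4 |
| QTc categories at first dose | Specified | Kept, through Table 2-10 |
| ECG abnormalities as adverse events | Specified in addition | Kept, for clinically significant findings (2.8.4.1) |
| ECG parameter statistics and change from pre-dose | Not in the first-dose sentence | Added (2.8.4.1, 2.8.5.4) |

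**Can the parameter statistics replace the missing row?** SAP 2.1 specifies mean, SD, median, minimum and maximum. As an illustration with assumed inputs, let 5 of 100 participants have a PR increase of 40 msec and the rest none:

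- mean change = (5 × 40 + 95 × 0) / 100 = 2 msec
- SD = √[(5 × 38² + 95 × 2²) / 99] = √(7600 / 99) ≈ 8.8 msec
- median 0, maximum 40 msec

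The maximum and SD would show that someone had a marked change. They would not state how many participants did, or whether any had AV block.

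**Can the adverse-event tables replace it?** They differ from the protocol item in three ways.

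1. *Selection.* Protocol 10.1.1 makes an abnormal test result an adverse event only if it causes signs or symptoms, is considered clinically significant, or needs therapy. Protocol 16.5 describes the day-1 second-degree type I block seen in earlier trials as transient and benign, so such a finding might not be reported.
2. *Timing.* SAP 2.8.1 tabulates "The number and percentage of subjects reporting any TEAEs" by age group, system organ class and preferred term from the first dose to the safety cutoff. Nothing separates the dosing day from the rest of the 24 months.
3. *Reference.* A treatment-emergent table has no pre-dose column, so it cannot give a pre-dose versus 6-hour comparison.

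**Can the dose-monitoring summary replace it?** SAP 2.8.5.3 summarizes yes/no items such as extended monitoring, hospitalization and permanent discontinuation. These are specific to the dose, but the examples given include no ECG finding.

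**What would the count tell us?** Exact (Clopper-Pearson) 95% limits for illustrative counts:

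- 0/100: upper limit 1 − 0.025^(1/100) = 3.6%
- 3/100: 0.6% to 8.5%
- 0/80: upper limit 1 − 0.025^(1/80) = 4.5%

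**The case against.** A reader might infer that first-dose AV block gets no incidence at all, and that the report could not say how many participants had a new conduction abnormality. The documents do not support that. Protocol 8.4.2 sends clinically significant ECG abnormalities to the adverse-event page. It also asks that any diagnosis associated with an abnormal ECG be recorded there, and that second instruction carries no clinical-significance condition of its own. A recorded AV block then gets n (%) by preferred term and by maximum severity, and appears in the listing of all adverse events. It may also appear in the special-interest tables, whose search terms are held outside these documents.

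A reader might also infer that only means are reported, so that a few large PR changes would go unseen. That fails too, because the maximum and SD are planned.

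The strongest remaining objection is that the omission may be declared. The body of SAP section 4, on changes to protocol-specified analyses, is redacted. The list in 2.8.5.4 is not worded as exhaustive, and neither the table shells nor the monitoring eCRF is shown. This limits the point to the visible text.

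There is also a fair objection to one remedy: a PR category alone does not identify second- or third-degree block, and the documents give no PR cut-off.

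What none of this supplies is a count tied to the first dose with a pre-dose comparison, which the protocol asks for in addition to the adverse-event summary.

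**Conclusion.** The point holds as a mismatch between protocol and SAP. The visible SAP omits one of the two first-dose ECG outputs in Protocol 12.5.1, the one that would cover conduction. First-dose AV block is counted through the treatment-emergent and possibly the special-interest tables, without a first-dose or pre-dose versus 6-hour incidence.

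The effect is confined to safety description; no efficacy result changes. No bias can be put in numbers, because the documents do not say how many 6-hour ECG abnormalities would go unreported as adverse events. The conclusion assumes that the redacted section 4 and the unseen shells neither add this output nor justify dropping it. If they do, the point is closed.

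**What to change.** Add to SAP 2.8.5.4 the n (%) of participants with abnormal ECG findings at pre-dose and at 6 hours after the first dose. Base it on data already captured:

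- a PR-interval category at each time point, with an age-appropriate cut-off that the sponsor prespecifies (the PR interval is on the eCRF under Protocol 8.4.2);
- AV-block diagnoses by degree from the adverse-event page, with onset on the dosing day.

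The second and restart doses, and exact 95% confidence intervals, are optional additions beyond the protocol sentence. If the output was dropped on purpose, section 4 should say so and give the reason.

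The cost is one extra safety table from ECGs already scheduled. Two limits should be stated with it. Any PR cut-off is a sponsor choice. The diagnosis rows still depend on adverse-event reporting and, with Protocol 10.1.1 asking for start and end dates, are specific to the dosing day rather than to the 6-hour ECG. The visible list of captured ECG parameters has no overall normal/abnormal field, so a broader count of abnormal ECGs would need such an item to exist on the eCRF.
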